### **3.1.4. Pharmacokinetic Analysis Set**

The Pharmacokinetic (PK) Analysis Set will include all enrolled subjects who took at least 1 dose of study drug and have at least 1 nonmissing postdose concentration value reported by the PK laboratory. This is the primary analysis set for all PK analyses.

### **3.1.5. Immunogenicity Analysis Set**

The Immunogenicity Analysis Set will include all subjects who took at least 1 dose of study drug and have at least 1 nonmissing postdose antidrug antibody (ADA) status reported. This is the primary analysis set for all immunogenicity analyses.

### **3.1.6. Biomarker Analysis Set**

The Biomarker Analysis Set will include subjects who took at least 1 dose of study drug and have at least 1 evaluable biomarker measurement available.

## **3.2. Subject Grouping**

Unless otherwise specified, subjects will be grouped by cohort for analyses:

- Cohort 1: 800 mg Q2W ADX monotherapy
- Cohort 2: combination therapy of ADX 800 mg Q2W with S-1 and cisplatin
- Cohort 3: combination therapy of ADX 1200 mg Q3W with S-1 and oxaliplatin
- Cohort 4: combination therapy of ADX 800 mg Q2W with nivolumab

For summaries where the cohorts will be aggregated, the summary results will be presented under the “Total” column.

## **3.3. Strata and Covariates**

This study does not use a stratified randomization schedule when enrolling subjects. No covariates will be included in analyses.

## **3.4. Examination of Subject Subgroups**

There are no prespecified subject subgroupings for analyses.

## **3.5. Multiple Comparisons**

Adjustments for multiplicity will not be made, because no formal statistical testing will be performed in this study.

### **3.6. Missing Data and Outliers**

#### **3.6.1. Missing Data**

In general, missing data will not be imputed unless methods for handling missing data are specified. Exceptions are presented in this document.

For missing last dosing date of study drug, imputation rules are described in Section 4.2.1. The handling of missing or incomplete dates for AE onset date is in Section 7.1.5.2, and for prior and concomitant medications in Section 7.4.

#### **3.6.2. Outliers**

Unless otherwise specified, outliers will not be excluded from the analysis in general.

### **3.7. Data Handling Conventions and Transformations**

The following conventions will be used for the imputation of date of birth when it is partially missing or not collected:

- If only month and year of birth is collected, then “15” will be imputed as the day of birth.
- If only year of birth is collected, then “01 July” will be imputed as the day and month of birth.
- If year of birth is missing, then date of birth will not be imputed.

In general, age (in years) on the date of the first dose of study drug will be used for analyses and presented in listings. If an enrolled subject was not dosed with any study drug, the enrollment date will be used instead of the first dosing date of study drug. For screen failures, the date the first informed consent was signed will be used for the age derivation.

Non-PK data that are continuous in nature but are less than the lower limit of quantitation (LOQ) or above the upper LOQ will be imputed as follows:

- A value that is 1 unit less than the LOQ will be used to calculate descriptive statistics if the datum is reported in the form of “< x” (where x is considered the LOQ). For example, if the values are reported as < 50 and < 5.0, values of 49 and 4.9, respectively, will be used to calculate summary statistics. An exception to this rule is any value reported as < 1 or < 0.1, etc. For values reported as < 1 or < 0.1, a value of 0.9 or 0.09, respectively, will be used to calculate summary statistics.
- A value that is 1 unit above the LOQ will be used to calculate descriptive statistics if the datum is reported in the form of “> x” (where x is considered the LOQ). Values with decimal points will follow the same logic as above.

- The LOQ will be used to calculate descriptive statistics if the datum is reported in the form of “ $\leq x$ ” or “ $\geq x$ ” (where x is considered the LOQ).

If methods based on the assumption that the data are normally distributed are not adequate, analyses may be performed on log-transformed data or nonparametric analysis methods may be used, as appropriate.

Natural logarithm transformation will be used for analyzing plasma concentrations and PK parameters. Plasma concentration values that are below limit of quantitation (BLQ) will be presented as “BLQ” in the concentration data listing. Values that are BLQ will be treated as 0 at predose time points, and one-half the value of the LOQ at postdose time points for summary purposes. The following conventions will be used for the presentation of summary and order statistics for PK concentrations:

- If at least 1 subject has a concentration value of BLQ for the time point, the minimum value will be displayed as “BLQ.”
- If more than 25% of the subjects have a concentration data value of BLQ for a given time point, the minimum and Q1 values will be displayed as “BLQ.”
- If more than 50% of the subjects have a concentration data value of BLQ for a given time point, the minimum, Q1, and median values will be displayed as “BLQ.”
- If more than 75% of the subjects have a concentration data value of BLQ for a given time point, the minimum, Q1, median, and Q3 values will be displayed as “BLQ.”
- If all subjects have concentration data values of BLQ for a given time point, all order statistics (minimum, Q1, median, Q3, and maximum) will be displayed as “BLQ.”

PK parameters that are BLQ will be imputed as one-half LOQ before log transformation or statistical model fitting.

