### **7.2.1. Summaries of Numeric Laboratory Results**

No summaries of numerical laboratory results will be provided.

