## 10. BIOMARKER ANALYSES

Binding of ADX to MMP9 will be evaluated in the periphery and additional biomarkers will be explored in blood and tumor tissue. A comprehensive analysis may be documented separately.

Biomarker Analysis Set will be used for biomarker analysis.

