### 10.1. Statistical Analysis Methods

All summaries will be presented in tabular or graphical form. Descriptive statistics refers to number of subjects, mean, median, standard deviation (StD), 1st quartile (Q1), 3rd quartile (Q3), minimum, and maximum for continuous measurements and number and percentage of subjects in each level of a categorical measurement.

Tables will be provided for the following:

- Descriptive Statistics for free and total MMP9 by visit for Cohort 1
- Descriptive Statistics for the baseline level for biomarkers including EBV, MMR, and PD-L1 for Cohort 4

Figures will be provided for the following:

- Mean ( $\pm$  StD) Plot for free and total MMP9 over time for Cohort 1
- Median (Q1, Q3) Plot for free and total MMP9 over time for Cohort 1

Listings will be provided for the following:

- Free and total MMP9 for Cohort 1
- EBV, MMR, and PD-L1 for Cohort 4

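### Under SAP 3.7, a free MMP9 result reported as below the LOQ enters the Cohort 1 summaries at close to the LOQ, which would raise the displayed mean, shrink the StD and leave the number of such values untold in the table and plots.

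*SAP*

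**What the plan says.** SAP 3.7 has separate below-LOQ rules for PK and non-PK data.

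- **Non-PK data.** The scope is "Non-PK data that are continuous in nature but are less than the lower limit of quantitation (LOQ) or above the upper LOQ". For a result reported as '< x', "A value that is 1 unit less than the LOQ will be used to calculate descriptive statistics". The worked examples are <50 and <5.0, where "values of 49 and 4.9, respectively, will be used to calculate summary statistics", and <1 and <0.1, where "a value of 0.9 or 0.09, respectively, will be used to calculate summary statistics".
- **PK concentrations.** Values below the LOQ count as 0 before dosing and as LOQ/2 after dosing. Order statistics are printed as BLQ in steps at 25%, 50% and 75%; the median step begins "If more than 50% of the subjects have a concentration data value of BLQ for a given time point". SAP 8.1.2 adds the number of subjects BLQ at each time point and leaves post-dose values at or below the LLOQ off the figures.

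Free MMP9 is a biomarker under SAP 10, where "Binding of ADX to MMP9 will be evaluated in the periphery". The only analyte in SAP Table 8-1 is ADX. SAP 10.1 plans "Descriptive Statistics for free and total MMP9 by visit for Cohort 1", a mean (± StD) plot, a median (Q1, Q3) plot and a listing. It states no below-LOQ convention, so the non-PK rule of SAP 3.7 applies by default.

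**The concern.** Andecaliximab binds MMP9 (Protocol 1.2.1), so the samples with the strongest binding are the ones most likely to have free MMP9 below the LOQ. Under SAP 3.7 those samples enter the summary near the top of the range in which they could lie.

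The rule matters mainly here. For safety laboratory data, SAP 7.2.1 states "No summaries of numerical laboratory results will be provided", so free and total MMP9 are the main by-visit numeric summaries that it governs. They are also the only displays of target engagement that the SAP commits to, because SAP 10 says only that a fuller analysis may be documented separately.

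With up to 6 subjects at 800 mg in Cohort 1 (SAP 1.3), a few substituted values can set the plotted centre and spread. SAP 10.1 asks for no count of them in the table or on the plots.

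**Working it through.** **1. Reproduce the SAP's examples.** Rule: LOQ minus one unit in the last reported digit, or 0.9 × LOQ where the LOQ is itself one unit.

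- <50: 49, and 49/50 = 0.98
- <5.0: 4.9, and 4.9/5.0 = 0.98
- <1: 0.9, and 0.9/1 = 0.90
- <0.1: 0.09, and 0.09/0.1 = 0.90

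All four match.

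**2. Dependence on reported precision.** The same rule gives <2 → 1 (50%), <5 → 4 (80%), <10 → 9 (90%) and <2.00 → 1.99 (99.5%). So 90% to 98% is the range of the examples, not a constant. At '<2' the rule coincides with LOQ/2.

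**3. Six subjects, LOQ 50.** The substitute is 49 under SAP 3.7 and 25 under LOQ/2, the SAP's own post-dose PK value. The measured values are assumptions.

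| Below LOQ | Measured | SAP mean (StD) | LOQ/2 mean (StD) | Median, SAP v LOQ/2 |
|---|---|---|---|---|
| 5 of 6 | 60 | 50.8 (4.5) | 30.8 (14.3) | 49 v 25 |
| 4 of 6 | 60, 80 | 56.0 (12.6) | 40.0 (24.1) | 49 v 25 |
| 3 of 6 | 60, 80, 100 | 64.5 (21.2) | 52.5 (32.7) | 54.5 v 42.5 |

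First row in full:

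- SAP mean: (5 × 49 + 60)/6 = 305/6 = 50.8
- SAP StD: √[(5 × 1.83² + 9.17²)/5] = 4.5
- LOQ/2 mean: (5 × 25 + 60)/6 = 185/6 = 30.8
- LOQ/2 StD: √[(5 × 5.83² + 29.17²)/5] = 14.3

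The median moves from three of six below the LOQ, where it averages the substitute and the lowest measured value. With two or fewer below, it is unaffected.

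**4. Direction against the true values.** Raising low values to a floor cannot widen the distance between any two subjects, so the StD cannot rise. A simulation of six lognormal values (log-scale SD about 0.7, assumed; units of the LOQ) gives the size:

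- True median 0.5 LOQ, about 84% of values below: true mean 0.64 and average StD 0.43. A substitute of 0.98 LOQ gives 1.07 and 0.18; LOQ/2 gives 0.67 and 0.32.
- True median equal to the LOQ, about 50% below: true 1.28 and 0.87. A substitute of 0.98 LOQ gives 1.46 and 0.70; LOQ/2 gives 1.22 and 0.89.

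In both cases LOQ/2 is closer to the truth on both statistics.

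**The case against.** The main objection is that nothing shows the rule will be triggered. The documents give no MMP9 LOQ, units, baseline level or reporting format, and the rule acts only on results reported as '< x'. This stands, and the point is therefore conditional.

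Several stronger readings are tempting, and the documents do not support them:

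- **That full suppression would be shown with false precision peculiar to this rule.** If all six values are below the LOQ, the StD is 0 under any single-value substitution, LOQ/2 included. What this rule adds is the high floor and the extra loss of spread when only some values are below.
- **That PK concentrations escape the problem.** Their BLQ display covers order statistics only; PK means and StDs still use fixed values.
- **That the reader cannot find the values below the LOQ.** SAP 10.1 plans a listing of free and total MMP9 for Cohort 1, and the substitution is stated for descriptive statistics only. The gap is in the table and plots.
- **That a percentage reduction would be misreported.** SAP 10.1 plans summaries of levels, with no percentage-reduction output.

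The stakes are also modest. Biomarkers are neither primary nor secondary endpoints (Protocol 8.1.2 and 8.1.3), no formal testing is planned (SAP 3.5), and the combination doses had been set by the review completed on 11 May 2017. The error understates suppression, so it would not create a false claim of target engagement. SAP 3.7 also allows log-transformed or nonparametric analyses, but neither removes the substituted values.

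**Conclusion.** The point holds in conditional form. By default, free MMP9 falls under a stated rule that places values below the LOQ at 90% to 98% of it in the SAP's examples. If free MMP9 is reported as '< x' after dosing, and at a precision that puts the substitute near the LOQ, then:

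- the displayed mean is too high whenever some subjects are below the LOQ;
- the median is too high once about half or more are below;
- the StD is too small when only some are below.

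In the assumed six-subject cases with three to five below an LOQ of 50, the mean is 12 to 20 units above its LOQ/2 value (64.5 − 52.5 = 12; 50.8 − 30.8 = 20). The StD is about one third to two thirds of its LOQ/2 value (4.5/14.3 = 0.31; 21.2/32.7 = 0.65). These sizes rest on assumed levels. At a reporting precision such as '<2' the difference from LOQ/2 disappears.

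The consequence is confined to a descriptive biomarker display in one small cohort. It does not reach the safety endpoint. It is worth correcting because the SAP already contains most of the better convention.

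**What to change.** In SAP 3.7 or 10.1:

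1. Exempt free MMP9, and total MMP9 for consistency, from the rule that substitutes one unit below the LOQ.
2. Use LOQ/2 for every value below the LOQ when computing the mean and StD, at all visits. Do not carry over the PK predose value of 0, because MMP9 is endogenous and can be present before dosing.
3. Print order statistics as BLQ at the 25%, 50% and 75% thresholds already set for PK concentrations.
4. Report the number of subjects below the LOQ at each visit in the table.
5. Where more than 50% are below the LOQ, omit the mean (StD) point and mark the median as BLQ.

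The cost is a few sentences in the SAP and reuse of the PK display logic, with no new data. If the SAP is already final, SAP 1 provides for recording the change in the CSR. The downside is that some visits will show BLQ instead of a number. LOQ/2 is itself a convention, so the count in item 4 is what lets the reader judge the rest.

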### **3.8. Analysis Visit Windows**

#### **3.8.1. Definition of Study Day**

Study day will be calculated from the date of first dose of study drug (ADX) administration and derived as follows:

- For post-dose study days: Assessment Date – First Dosing Date + 1
- For days prior to the first dose: Assessment Date – First Dosing Date

Therefore, study day 1 is the day of first dose of ADX administration.

### **3.8.2. Analysis Visit Windows**

The nominal visit as recorded on the case report form (CRF) will be used when data are summarized by visit.

Any data relating to unscheduled visits will not be assigned to a particular visit or time point. However, the following exceptions will be made:

- An unscheduled visit prior to the first dosing of study drug may be included in the calculation of the baseline value, if applicable.
- Unscheduled visits after the first dosing of study drug will be included in determining the maximum postbaseline toxicity grade.
- Data collected on an end of treatment (EOT) visit will be summarized as a separate visit, labeled as “End of Treatment Visit”.
- Data collected on an EOS visit will be summarized as a separate visit, labeled as “End of Study Visit”.
- Data collected on a 30-day safety follow-up visit will be summarized as a separate visit, labeled as “30-Day Safety Follow-Up Visit”.
- Data collected on a 5-month safety follow-up visit will be summarized as a separate visit, labeled as “5-Month Safety Follow-Up Visit”.

## 4. SUBJECT DISPOSITION

### 4.1. Subject Enrollment and Disposition

A summary of subject enrollment will be provided by cohort for each investigator and overall. The summary will present the number and percentage of subjects enrolled. For each column, the denominator for the percentage calculation will be the total number of subjects analyzed for that column.

A summary of subject disposition will be provided by cohort and overall, as appropriate. This summary will present the number of subjects screened and the number of subjects enrolled, and the number of subjects in each of the categories listed below:

- Safety Analysis Set
- Treated with study drug (ADX) (all cohorts)
  - Treatment discontinued
    - Reasons for discontinuation
- Treated with S-1 (cohorts 2 and 3)
  - Treatment discontinued
    - Reasons for discontinuation
- Treated with oxaliplatin (cohort 2)
  - Treatment discontinued
    - Reasons for discontinuation
- Treated with cisplatin (cohort 3)
  - Treatment discontinued
    - Reasons for discontinuation
- Treated with nivolumab (cohort 4)
  - Treatment discontinued
    - Reasons for discontinuation
- Completed lesion assessment
- Discontinued lesion assessment before disease progression

#### Reasons for lesion assessment discontinuation

- Discontinued study (including long-term follow-up for overall survival)

#### Reasons for study discontinuation

For the status of study drug, lesion assessment completion, study completion and reasons for premature discontinuation, the number and percentage of subjects in each category will be provided. The denominator for the percentage calculation will be the total number of subjects in the Safety Analysis Set corresponding to that column. In addition, a flowchart will be provided to depict the disposition.

The following by-subject listings will be provided by subject identification (ID) number in ascending order to support the above summary tables:

- Reasons for premature study drug or study discontinuation
- Reasons for screen failure (will be provided by screening ID number in ascending order)

### **4.2. Extent of Study Drug Exposure**

Extent of exposure to study drug will be examined by assessing the total duration of exposure to study drug specified in the protocol.

#### **4.2.1. Exposure to Study Drug (ADX)**

Exposure to ADX will be summarized by cohort for the Safety Analysis Set.

#### **Duration of Exposure**

Duration of exposure to study drug will be defined as (last dose date - first dose date + 1), regardless of temporary interruptions in study drug administration, and will be expressed in weeks using up to 1 decimal place (eg, 4.5 weeks). If the last study drug dosing end date is missing, the last study drug start date will be used to impute the end date of the last study drug.

Duration of exposure to ADX will be summarized using descriptive statistics.

#### **Number of Doses**

The total number of doses of ADX that each subject received during the study will be summarized using descriptive statistics. A subject is said to have received a dose of ADX if he/she received any amount of the planned dose of ADX (ie, actual dose > 0) at a visit. Additionally, the number and percentage of subjects receiving a given number of doses category will be summarized, as appropriate.

### **Actual Dose Amount**

In addition, the total and average actual dose amount of ADX in mg that each subject received will be summarized using descriptive statistics.

The average actual dose amount of ADX is defined as (total actual dose amount received in mg) / (number of doses given), regardless of whether the doses were interrupted/completed or full/reduced.

A by-subject listing of study drug (ADX) administration will be provided by subject ID number (in ascending order) and visit (in chronological order), including dosing date/time, planned dosage, actual dosage administered, infusion outcome and reason for dose interruption (if applicable).

#### **4.2.2. Exposure to Chemotherapy**

Exposure to chemotherapy agents, including cisplatin, oxaliplatin and nivolumab, will be listed. Duration of exposure and the total number of doses that each subject received during the study will be summarized for each agent in a similar manner as for ADX. Chemotherapy received prior to study enrollment and after the start of other anti-cancer therapy will not be included in the summary.

S-1 was administered orally twice daily. A by-subject listing of S-1 administration will be provided by subject ID number (in ascending order), including dose per administration, dose frequency, start and stop date, and reason for dose interruption or modification (if applicable).

#### **4.2.3. Exposure to Nivolumab**

Exposure to nivolumab will be listed. Duration of exposure to nivolumab and the total number of doses of nivolumab that each subject received during the study will be summarized in a similar manner as for ADX.

### **4.3. Protocol Deviations**

Subjects who did not meet the eligibility criteria for study entry but were enrolled in the study will be summarized regardless of whether they were exempted by the sponsor or not. The summary will present the number and percentage of subjects who did not meet at least 1 eligibility criterion and the number of subjects who did not meet specific criteria by cohort and overall for the All Enrolled Analysis Set. A by-subject listing will be provided for those subjects who did not meet at least 1 eligibility (inclusion or exclusion) criterion. The listing will present the eligibility criterion (or criteria if more than 1 deviation) that subjects did not meet and related comments, if collected.

Protocol deviations occurring after subjects entered the study are documented during routine monitoring. The number and percentage of subjects with important protocol deviations by deviation reason (eg, nonadherence to study drug, violation of select inclusion/exclusion criteria) will be summarized by cohort and overall for the All Enrolled Analysis Set. A by-subject listing will be provided for those subjects with important protocol deviation.

## **5. BASELINE CHARACTERISTICS**

### **5.1. Demographics and Baseline Characteristics**

Subject demographic variables (ie, age, sex, race, and ethnicity) and baseline characteristics (body weight [in kg], height [in cm], body mass index [BMI; in kg/m^2]) will be summarized by cohort and overall using descriptive statistics for continuous variables and using number and percentage of subjects for categorical variables. The summary of demographic data will be provided for the Safety Analysis Set.

A by-subject demographic listing, including the informed consent date, will be provided by subject ID number in ascending order.

### **5.2. Other Baseline Characteristics**

No other baseline characteristics will be summarized.

### **5.3. Medical History**

Medical history will be collected at screening for disease-specific and general conditions (ie, conditions not specific to the disease being studied).

Disease-specific medical history will be summarized for the variables listed below, by cohort and overall by the number and percentage of subjects with each prepopulated condition. The summary will be provided for the Safety Analysis Set. No formal statistical testing is planned.

Variables to be summarized include:

- Type of cancer
- Pathological subtype of gastric cancer
- Disease stage at diagnosis
- Disease stage at screening
- Differentiation
- Time since diagnosis

The denominators for the percentage will be the numbers of subjects in the Safety Analysis Set corresponding to that column, except that for pathological subtype of gastric cancer, percentages will be calculated based on the number of subjects with gastric cancer in that column.

A by-subject listing of disease-specific medical history will be provided by subject ID number in ascending order.

General medical history data will be collected at screening and listed only. General medical history data will not be coded.

